attainment, 3) acceptability (Intrinsic Motivation Inventory – Interest/Enjoyment Subscale¹⁰), and Adverse & Serious Adverse Events (Timed Up-and-Go, Falls Efficacy Scale-International, Frequency of Events). Aim 2 outcomes, to assess effect size, will be average 10-day physical activity counts (ActiGraph monitors^{2, 11}) and self-report disability (Late-Life Function and Disability Index (LLFDI)^{12, 13}). In addition, Baseline descriptive measures include demographics, medications, cognition (Folstein Mini-Mental State Exam¹⁴), depression (Geriatric Depression Scale SF^{15, 16}), residual limb quality (Chakrabarty Scale¹⁷), sensory testing (Michigan Neuropathy Screen^{18, 19}), social support (Multidimensional Scale of Perceived Social Support), exercise readiness to change (Exercise Stages of Change^{20, 21}), prosthesis description, and comorbidities (Functional Comorbidity Assessment²²).

[figure not shown]

Fig. 1. Crossover study design.

Interventions and Duration

Thirty-two participants will be randomly assigned to two groups: GROUP1 or GROUP2. The home-based study design is intended to reduce participant burden by removing transportation and time barriers. There will be two participation periods of three months (Months 1-3 and 4-6). PABC intervention will occur Months 1-3 for GROUP1 and Months 4-6 for GROUP2. GROUP2 will participate in a no-exercise, attention control in Months 1-3. GROUP1 will have a no contact, intervention “wash-out” period in Months 4-6.

Evaluations will take place using the following schedule:

Baseline only: At Baseline testing, participants will also complete the following tests/measures/forms:

- 1) Folstein Mini-Mental State Examination
- 2) Geriatric Depression Scale SF
- 3) Chakrabarty scoring of residual-limb quality
- 4) Michigan Neuropathy Screen
- 5) Prosthetic description and Demographic Form
- 6) Functional Comorbidity Index
- 7) Multidimensional Scale of Perceived Social Support

Baseline, 3 and 6 months:

- 1) Timed Up-and-go
- 2) Two Minute Walk Test
- 3) Five Meter Walk
- 4) Single Limb Stance Test
- 5) Falls Efficacy Scale-International
- 6) Activity Measurement
- 7) Self-Efficacy for Exercise Scale
- 8) Intrinsic Motivation Inventory (IMI) – Interest/Enjoyment Subscale
- 9) LLFDI
- 10) Exercise Stages of Change
- 11) Prosthesis Evaluation Questionnaire – Mobility Section

Continuously: Falls, Adverse Events (AEs), and Serious Adverse Events (SAEs) will be recorded and reported as needed.

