We will recruit older Veterans with dysvascular LLA (1-5 years after LLA) to participate in the PABC intervention, which uses established VA Health Care system technology and evidence-based intervention methods. The five key dimensions of feasibility to be assessed are whether Veterans: 1) can successfully participate in the intervention (practicality), 2) tolerate physical activity progression (implementation feasibility), 3) are interested and enjoy the intervention (acceptability), 4) complete the intervention safely (safety), and 5) respond to the intervention with increased activity and decreased disability (responsiveness).^{31,32} Measures of physical activity and disability will be used to establish effect size estimates for the PABC intervention, with the intention of planning a future clinical efficacy trial. Testing will occur at baseline (pre-intervention), three months (end of intervention), and six months, using a two-group randomized crossover design.

Primary Aim: Determine feasibility of using the PABC intervention with older Veterans who have dysvascular LLA by assessing: 1) practicality (measured by retention rate), 2) implementation feasibility (measured by dose goal attainment), 3) participant acceptability (measured by the Intrinsic Motivation Inventory (IMI) – Interest / Enjoyment Subscale), and 4) safety (measured with Adverse and Serious Adverse Events).

Hypothesis 1.1: Retention rate will be at least 85% over the PABC intervention period (i.e., ≤15% attrition).

Hypothesis 1.2: At least 75% of participants will meet the dose goal of a 3% average increase in daily steps per week, across the three months of intervention.

Hypothesis 1.3: Participants will indicate PABC intervention acceptability with a mean score of ≥ 5/7 on the IMI – Interest / Enjoyment Subscale.

Hypothesis 1.4: There will be similar rates of study related (definitely, probably, possibly) adverse events between groups during the first three months (period of direct comparison of intervention versus control).

Secondary Aim: Establish effect size estimates of the PABC intervention (responsiveness)

using physical activity and self-report disability outcomes.

Hypothesis 2.1: The PABC group will have increased activity counts and less self-reported disability than the control group at Month 3, each with effect size estimates ≥ 0.80 (Cohen's d).

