Hypothesis 2.2: Mean and standard deviation values for activity counts (accelerometer-based activity monitors) and disability (Late-Life Function and Disability Index) will allow for sample size estimates for the subsequent larger efficacy trial.

Impact: This pilot study addresses an understudied and growing population of older Veterans characterized by complex health conditions, compounded by chronic low physical activity and high levels of disability. This novel trial will be the first to specifically target chronic physical inactivity behavior for Veterans living with dysvascular LLA. The outcome will significantly advance current research by 1) characterizing the feasibility of using the PABC intervention and 2) establishing an intervention effect size estimate to guide future trials.

B. Background and Significance:

B.1. Significance

This pilot study is significant for Veterans with dysvascular LLA, based primarily on: 1) a high prevalence of dysvascular LLA, 2) poor long-term physical activity outcomes, 3) limited evidence-based physical activity rehabilitation strategies, and 4) barriers to accessing rehabilitation clinicians.

Dysvascular Amputation: Amputation caused by severe diabetes mellitus (DM) with dense sensory and motor neuropathy leading to a non-healing foot wound or severe peripheral artery disease (PAD) with critical limb ischemia (or a combination of these two related but separate pathophysiologies).

High prevalence of dysvascular amputation

The number of Veterans with dysvascular LLA is increasing. The number of people living with amputation in the United States is projected to be 2.3 million in 2050 ($\approx 100\%$ increase from current value), due to an aging population and increased prevalence of underlying causes such as DM and PAD.²³ Although there is a current trend of decline in total amputation rate among Veterans, there is a growing population of Veterans with dysvascular LLA. For example, from 2000 to 2004 there was a 34% decrease in relative amputation rate (amputation/DM Veteran population).³³ However, due to an increase in number of Veterans with DM during the same time period, the population of Veterans with diabetes and initial LLA increased by 23%.³³

Poor long-term physical activity and disability outcomes

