Our research team has worked with outpatient rehabilitation clinics in four regional hospitals on the front-range of Colorado, including the Denver VAMC, to develop and implement a standardized battery of rehabilitation outcome measures for patients with LLA. In our recent analysis, patients with dysvascular LLA at all hospitals improved physical function with rehabilitation.^{53, 72} Despite improvements, functional outcomes remained below clinically important cut-off scores. For example, gait speeds <0.8 m/s indicate low life expectancy and poor ability for community ambulation.^{73, 74} In our sample (n=42) at rehabilitation discharge, 45% of patients had gait speeds <0.8 m/s. Additionally, Timed Up-and-Go (TUG) test times >19 s indicate high risk for multiple falls after LLA.⁷⁵ Thirty-two percent of participants had discharge TUG times >19 s. These results demonstrate that despite improvements during rehabilitation, the risks of inactivity and falls are high following dysvascular LLA.

C.2. Functional training and participation-based rehabilitation following dysvascular LLA: a case series

We have conducted a prospective case-series (n=3) examining progressive outpatient rehabilitation after dysvascular LLA. The aims of the case-series were to: 1) describe progressive functional training and participation-based rehabilitation after dysvascular LLA, 2) describe the complex medical conditions of patients with dysvascular LLA, and 3) determine the persistence of functional improvements across the first year after LLA. Each patient in this case series had large functional gains during rehabilitation. However, all three patients rated their physical function lower (10-50%) at a seven-month follow-up than at the time of rehabilitation discharge. In addition, two of the three patients developed a new diabetic foot ulcer on the limb opposite the amputation by the seven-month follow-up. These poor functional outcomes are consistent with other studies,^{27, 30, 76} further supporting the need to identify strategies to improve long-term function and activity.

C.3. Collaborative-care, home intervention for improving physical function following dysvascular LLA

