- H1.1) Retention rate will be assessed using a cut off of 15% attrition (i.e., loss of >6 participants). Mean attrition rate will be compared to the null value of 15% using a one-sample t-test ($\alpha=0.05$). This attrition rate is considered feasible based on previous activity change programs for patients with DM or PAD.^{5, 83}
- H1.2) Dose goal attainment will be assessed by the proportion of participants achieving the goal of 3% average weekly increase in steps, based on activity gains in other intervention studies.^{3, 12, 78} The ability to attain a 3% average weekly step increase for <75% of the participants will be considered a negative result. The proportion of participants attaining a 3% average weekly step increase will be reported (95% CI) and compared to the null value of 75% using a one-sample binomial proportions test ($\alpha=0.05$).
- H1.3) Acceptability of the intervention will be measured with the IMI Interest and Enjoyment subscale, with a mean score of <5/7 considered a negative acceptability result.¹⁰ Mean IMI Interest and Enjoyment score will be compared to the null value of 5.0 using a one-sample t-test ($\alpha=0.05$).
- H1.4) Adverse and serious adverse event (AE/SAE) rates (events/participant) will be compared between groups for Months1-3 (PABC intervention for GROUP1, attention control for GROUP2). We expect similar AE/SAE rates between groups (assessed by Safety Officer and research team).

Aim 2 (Effect Size and Preliminary Efficacy of PABC Intervention): Effect size of the PABC intervention will be calculated with Cohen's d using mean and standard deviation for change in activity counts and LLFDI scores. Statistical inference of group differences for calculation of sample size estimates will be based on linear models with activity counts and LLFDI scores as outcome variables. Explanatory variables in each model will include primary medical diagnosis (PAD, DM, or both), group, and baseline activity count or LLFDI score.

D.10. Expected Outcomes and Interpretation

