Determining feasibility of the PABC intervention will set the stage for implementing a larger efficacy study. The expected result is that Veterans with LLA can be enrolled and retained in the PABC intervention with adherence to a 3% weekly increase in physical activity dose. In addition, the effect size is expected to be ≥ 0.80 . While similar interventions have been feasible and successful for other chronic disease populations, this trial will be the first to target chronic physical inactivity behavior for Veterans living with dysvascular LLA.

D.11. Participant Safety

Anticipated adverse events include falls and medical complications due to DM and PAD. A Safety Officer ([name]) for the study will meet with the PI quarterly to review study progress and adverse events. [name] is the Outpatient Medical Director for Rehabilitation Services at the Denver VAMC. [name] is also an Associate Professor in the Department of Physical Medicine and Rehabilitation at the University of Colorado. Beyond his clinical expertise, [name] has experience in outcomes research related to patients with LLA and functional exercise interventions. Fall risk will be monitored using the TUG test and Falls Efficacy Scale-International (FES-I) at all test points (baseline, 3M, 6M). Also, occurrence of falls will be recorded at each of weekly visit in both the intervention and control periods. Fall occurrences and other adverse events will be reported on a quarterly basis to the Safety Officer. The incidence of falls, defined as “inadvertently coming to rest on the ground, floor or other lower level, excluding intentional change in position”,⁸⁴ will be of particular focus. All study-related falls (possibly, probably, or definitely) will be tracked. If the total number of falls reaches 4, the Safety Officer will review incidence by group. If the number of falls for the intervention group exceeds that of the control group by 3 (10% of enrollment) at any time, the study will be suspended until an evaluation of study relatedness for each incidence is performed by the Safety Officer.

D.12 Potential Pitfalls and Alternative Strategies

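### H1.4 judges safety on overall AE/SAE rates with no event-class comparison or interval, so an excess of limb wounds under PABC can be masked by other events

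*Combined protocol and SAP*

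**What the plan says.** Safety is one of the four Primary Aim hypotheses. Section A words H1.4 as "There will be similar rates of study related (definitely, probably, possibly) adverse events between groups during the first three months". D.9 describes the analysis as "Adverse and serious adverse event (AE/SAE) rates (events/participant) will be compared between groups for Months1-3", adding "We expect similar AE/SAE rates between groups (assessed by Safety Officer and research team"). D.9 does not repeat the restriction to study-related events. It gives no margin, interval, test or alpha for H1.4, whereas H1.1 to H1.3 each have a named test, a null value and an alpha.

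D.11 sets out what is expected: "Anticipated adverse events include falls and medical complications due to DM and PAD". Fall incidence "will be of particular focus". Falls get a formal definition, weekly recording in both periods, a by-group review once the total reaches 4, and suspension if the intervention group exceeds control by 3.

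Limb wounds get none of this. The only limb-condition item in the Synopsis schedule, "Chakrabarty scoring of residual-limb quality", is in the list done at baseline only. The 3- and 6-month battery has no skin or limb examination. After baseline, a wound enters the data only as an adverse event, recorded continuously or at the weekly video contact (Table 2).

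**The concern.** The team had reason to name wounds as an event class. In its own case series (C.2), "two of the three patients developed a new diabetic foot ulcer on the limb opposite the amputation by the seven-month follow-up". B.1 describes one route to dysvascular amputation as "dense sensory and motor neuropathy leading to a non-healing foot wound", so wounds belong to the disease under study, and self-report may be incomplete in participants with that neuropathy.

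H1.4 adds wounds to every other AE and SAE and then asks whether the totals look similar. If other events are common, a multiple of the wound rate becomes a modest ratio in the total, with more random noise around it. The pilot could then report similar safety, and the planned efficacy trial would start without a visible wound count by group.

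**Working it through.** **The plan's own figures.** H1.4 has no event rate, margin, power or alpha, so there is nothing to reproduce for safety. The only power figure is for Aim 2 in D.8 (26 completers, d = 0.8, two-sided 0.05, paired t test, above 95%). Noncentral t gives 97.5%, which agrees but does not bear on H1.4.

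**Inputs.**
- From the documents: 32 participants in two groups, 16 in GROUP1; comparison over Months 1-3.
- Assumed, because the documents give no rates: Poisson events; control wound rate c = 0.10 per participant; fold excess k = 4, so 0.40 under PABC; b other events per participant, equal in both groups.

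**Dilution of wounds.** Pooled ratio = (b + kc)/(b + c). Expected counts are 16 times each rate. The last column is the exact Poisson probability that the PABC count is no larger than the control count.

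| b | Pooled ratio | Expected events, PABC vs control | P(PABC looks no worse) |
|---|---|---|---|
| 0 (wounds alone) | 0.40/0.10 = 4.00 | 6.4 vs 1.6 | 5.6% |
| 0.10 | 0.50/0.20 = 2.50 | 8.0 vs 3.2 | 9.5% |
| 0.25 | 0.65/0.35 = 1.86 | 10.4 vs 5.6 | 13.9% |
| 0.50 | 0.90/0.60 = 1.50 | 14.4 vs 9.6 | 18.9% |
| 1.0 | 1.40/1.10 = 1.27 | 22.4 vs 17.6 | 24.8% |
| 2.0 | 2.40/2.10 = 1.14 | 38.4 vs 33.6 | 30.6% |

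The absolute difference is 0.30 per participant in every row. What changes is the noise. The standard error of the difference is √(total expected events)/16, which is √8/16 = 0.18 for wounds alone and √40/16 = 0.40 at b = 1.0.

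**Falls under D.11.** I simulated the running difference in falls over Months 1-3, with 16 per group, Poisson counts and all falls counted.

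| Falls per participant, control vs PABC (threefold) | P(excess reaches 3) | P(total reaches 4) |
|---|---|---|
| 0.05 vs 0.15 | 32% | 40% |
| 0.10 vs 0.30 | 66% | 88% |
| 0.20 vs 0.60 | 91% | above 99% |
| 0.25 vs 0.75 | about 95% | above 99% |

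Other adverse events do not affect these probabilities. The H1.4 ratio is still diluted: for 0.25 vs 0.75 at b = 1.0 it is 1.75/1.25 = 1.40.

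**What separate reporting can deliver.** At the expected wound counts, the difference is 0.30 with an approximate 95% CI of 0.30 ± 1.96 × 0.177, or −0.05 to 0.65. An exact conditional test (two-sided 0.05) has 26% power on wounds alone, against 9% on the pooled count at b = 1.0. Separate reporting makes the signal visible but does not settle it.

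**The case against.** The strongest reply is that Section A limits H1.4 to study-related events, which would remove much of the unrelated disease background. This largely stands. At b of 0.10 to 0.25 the pooled ratio is 2.50 to 1.86, and the chance of looking no worse is 9.5% to 13.9%, not 24.8%. But D.9, where the analysis is defined, does not carry the restriction, and only zero background removes the dilution entirely.

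Second, D.11 handles falls. As monitoring, it mostly does. A reader might infer that a several-fold excess of falls would go unseen. The documents do not support that: by-group review or suspension would usually be triggered at control rates of about 0.1 or more per participant, though less reliably at 0.05. What remains is that D.11 prompts review and does not enter the H1.4 conclusion.

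Third, wounds are not unrecorded. They can be reported as AEs, and events other than falls also go to the Safety Officer quarterly. That stands, but no wound count or by-group comparison is specified.

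Fourth, a reader might take the case series as evidence that more stepping causes ulcers. It is not: C.2 reports three patients, with ulcers appearing alongside declining self-rated function. Nor does the neuropathy phrase in B.1 describe every participant, since D.3 admits diabetes and/or arterial disease.

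Fifth, 16 per group is too few for event-specific inference. This is correct, and it limits what the fix can claim.

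**Conclusion.** The point holds in a limited form. H1.4 rests a primary safety conclusion on overall AE/SAE rates, judged similar without a criterion, an event-class comparison or an interval. A fourfold wound excess (0.10 to 0.40 per participant, 16 per group) would appear as a pooled ratio of 1.27 with 1.0 other event per participant, and 1.86 with 0.25. These sizes depend wholly on assumed rates and on Poisson counts.

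The gap is mainly for wounds, which have no separate count, comparison or follow-up measure. For falls it is narrower: the data and by-group monitoring exist, but the result is not tied to H1.4. A reader might also infer that repeating the residual-limb score would close the gap. It would not, because the ulcers in C.2 were on the opposite limb, which that score does not cover.

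**What to change.** In D.9 under H1.4:

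- Keep the overall AE/SAE rate for Months 1-3.
- Add two pre-named comparisons for the same period: falls, and new lower-extremity wounds or ulcers on either limb. For each, report participants affected, the rate by group, and the between-group difference with a 95% CI.
- Show each for all events and for study-related events, and reconcile Section A (study-related events) with D.9 (all AEs and SAEs) by stating which set H1.4 uses.
- State that the intervals will be wide at 16 per group, and that similar safety may not be concluded from the overall rate alone.

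The cost is a few sentences and two small tables, using falls and AE data already recorded. No visit, measure or clinical rule changes. The drawback is two more imprecise comparisons, which should be presented as descriptive estimates for planning the efficacy trial and not as proof of safety.

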The proposed pilot study is a randomized, tester-blinded design assessing PABC intervention feasibility (Aim 1) and effect size (Aim 2). Randomization ($n=32$) will create two groups (GROUP1 or GROUP2) using computer-generated random blocks of 2 and 4, stratified by amputation level (transtibial and transfemoral). An investigator not involved with testing or intervention ([name]) will conceal group allocation. A crossover design is used to simultaneously accomplish the aims and optimize recruitment (Fig.2). The PABC Intervention will be delivered to both groups (GROUP1 during Months 1-3 and GROUP2 during Months 4-6). The crossover design provides $n=32$ for assessing Aims 1 and 2. Intervention effect retention will be tested at six months for GROUP1 ($n=16$).

D.1. Setting

The study will occur at the VA Geriatric Research Education and Clinical Center (GRECC), where Drs. [name] and [name] have dedicated positions ([name] (GRECC Director)). Intervention delivery will occur with the participant at home and therapist at a VA site with access to tablet interface software (e.g. VA Jewell Motion Analysis Lab or VA Clinical Building South, using VA-supplied and approved mobile-health tablets and wearable activity sensors (FitBit)).

D.2. Participants

Thirty-two participants will be recruited from the Denver VAMC. The target sample is older Veterans diagnosed with PAD and/or DM, who have major LLA. We expect $<15\%$ attrition, with a goal of 26 participants completing.

D.3. Eligibility Criteria

Inclusion criteria: ≥ 50 years of age, LLA 1-5 years prior, Type II DM and/or PAD, and

ambulatory without human assistance, in the home or better using a prosthesis, with assistive device as needed, with assistive device as needed. Exclusion criteria: wheelchair as primary form of locomotion, trauma or cancer-related etiology of the LLA, unstable heart condition, uncontrolled hypertension, acute systemic infection, cancer, recent stroke (within 2 years), or lower extremity wound or ulcer that limits ambulation.

D.4. Recruitment Strategies

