All participants will be recruited from the Denver VA Medical Center (VAMC) or Veterans that are receiving care outside of the VA system in our core-group of regional hospitals. [name] and [name] will use the Amputation Clinic database and meet with the rehabilitation teams to obtain names of Veterans meeting the inclusion criteria. A research team member will then contact the potential participant in person or by letter and ask for permission to explain and complete a brief screening form to determine the Veteran's eligibility. We will increase the recruitment pool for this study from our previous studies, by allowing participants with both transfemoral and transtibial amputation. Recruitment from the Denver VAMC is expected to be feasible based on Denver VAMC data (47 new Veterans seen in rehabilitation for new major LLA in last 18 months).

D.5. Intervention

The home-based study design is intended to reduce participant burden by removing transportation and time barriers. There will be two participation periods of three months (Months 1-3 and 4-6). PABC intervention will occur Months 1-3 for GROUP1 and Months 4-6 for GROUP2 (Fig.1). GROUP2 will participate in a no-exercise, attention control in Months 1-3. GROUP1 will have a no contact, intervention "wash-out" period in Months 4-6.

Study Initiation. A physical therapist will initially meet with the participant at the participant's home to: 1) obtain informed consent and authorization, 2) deliver and orient the participant to wearing an activity monitor (ActiGraph Inc. Pensacola FL), and 3) assess the prosthetic fit and function (Prosthetic Evaluation Questionnaire). If prosthetic fit and function concerns are identified, the participant will be given recommendations for seeing his/her prosthetist, which must be met before beginning the intervention. The participant will wear the ActiGraph monitor for 10 days after the initial visit. The ActiGraph monitor will be used only for outcome data (not intervention) and provides no feedback to participants.

Following the initial visit, participants will be randomized (GROUP1 and GROUP2).

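### The only planned safety analysis covers Months 1-3, so half of the planned PABC exposure (GROUP2, Months 4-6) enters no event-rate estimate; a descriptive on-PABC rate should be added beside H1.4

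*Combined protocol and SAP*

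**What the plan says.** Section A poses the safety question as whether Veterans "complete the intervention safely (safety"). H1.4 there predicts similar rates of study-related adverse events "between groups during the first three months (period of direct comparison of intervention versus control"). Section D.9 repeats the window: event "rates (events/participant) will be compared between groups for Months1-3 (PABC intervention for GROUP1, attention control for GROUP2"). It names no test, margin or threshold and leaves the judgement to the Safety Officer and the research team. D.9 contains no other safety analysis.

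The opening of section D says: "The PABC Intervention will be delivered to both groups (GROUP1 during Months 1-3 and GROUP2 during Months 4-6"). It adds: "The crossover design provides $n=32$ for assessing Aims 1 and 2". The same paragraph gives the size of one group: "Intervention effect retention will be tested at six months for GROUP1 ($n=16").

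On data collection, the Synopsis has falls, AEs and SAEs recorded continuously. Section D.11 says that "occurrence of falls will be recorded at each of weekly visit in both the intervention and control periods", with quarterly reports to the Safety Officer and a suspension rule based on the difference in falls between groups.

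**The concern.** Whether participants complete PABC safely is a question about everyone who receives PABC. Of the four Aim 1 hypotheses, only safety is confined to Months 1-3. In section A, retention is framed over the PABC period, dose attainment across the three intervention months, and acceptability as acceptability of the intervention. Feasibility could therefore be described on up to 32 treated people, while the planned safety result draws its on-PABC information from 16.

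At stake is how much the pilot can say about the frequency of events on PABC, which a larger trial will need. D.11 expects falls and complications of DM and PAD. As the plan stands, any summary of GROUP2's PABC months would be chosen after the data are seen.

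**Working it through.** **The plan's own figures.** The plan gives no sample size, margin or precision for H1.4. Its one power statement (D.8) concerns efficacy. It reproduces: effect size 2000 × 0.03 × 12 / 900 = 0.80, and a two-sided paired t test with n = 26 at α = 0.05 has 97.5% power, consistent with the stated value above 95%. It has no bearing on safety. The relevant figure is the n = 32 claimed for Aim 1.

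**Inputs.** 32 participants, 16 in GROUP1 (section D), hence 32 − 16 = 16 in GROUP2. For the period length, D.5 says: "There will be two participation periods of three months (Months 1-3 and 4-6"). Expected completers are 26, or 13 per group (D.8).

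**Exposure.**
- Planned PABC exposure: 32 × 3 = 96 person-months.
- Inside the H1.4 window: 16 × 3 = 48 (50%).
- Outside it (GROUP2, Months 4-6): 48 (50%).
- If all 16 in GROUP1 start PABC but only 13 or 14 of GROUP2 do, the excluded share is 13/29 = 45% or 14/30 = 47%.

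H1.4 does use all 32 participants, as 16 versus 16, but only 16 of them are on PABC in the window.

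**Zero-event upper bound**, one-sided 95%, 1 − 0.05^(1/n):

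| PABC-exposed n | Upper bound |
|---|---|
| 16 | 17.1% |
| 32 | 8.9% |
| 13 | 20.6% |
| 26 | 10.9% |

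**Chance of seeing at least one case**, 1 − (1 − p)^n. The documents give no event risks, so p is an assumption shown over a range:

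| Assumed risk p | n = 16 | n = 32 |
|---|---|---|
| 2% | 27.6% | 47.6% |
| 5% | 56.0% | 80.6% |
| 10% | 81.5% | 96.6% |

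With 13 and 26 completers the 5% row becomes 48.7% and 73.6%.

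These figures describe a single-group on-PABC estimate. They do not describe the precision of the randomised difference in H1.4, which GROUP2's later months cannot improve. The zero-event bound is most relevant to less common event types, since some falls are expected.

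**Which events count.** Section A limits H1.4 to events definitely, probably or possibly related to the study. D.9 states AE and SAE rates without that limit. An added estimate has to say which set it uses.

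**Recording by period.** D.11 documents weekly recording of falls in both the intervention and control periods. Weekly recording of falls and adverse events together appears only in the PABC visit content (Table 2). The description of the control period in D.5 does not mention adverse-event recording.

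**The case against.** The Months 1-3 window is deliberate, and section A gives the reason: it is when intervention and control are compared directly. In Months 4-6 GROUP1 is in a no-contact wash-out, so no concurrent attention control exists. This stands in full, and H1.4 should not be widened or replaced. It justifies the comparison, but it is no reason to omit an estimate of the on-PABC rate.

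A reader might infer that GROUP2's events on PABC are ignored, or that PABC could be declared safe against the trial's own data. The documents do not support that. Events are recorded continuously, the Safety Officer sees them quarterly, and the falls rule applies at any time. H1.4 has no threshold, and nowhere is the safety conclusion said to rest on it alone. What remains is that monitoring yields no pre-specified estimate.

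A reader might also infer that H1.4 contradicts the n = 32 statement. It does not do so outright: all 32 enter the comparison, and the sentence covers Aims 1 and 2 together without promising 32 PABC-exposed people for every hypothesis.

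The Synopsis also lists the Timed Up-and-Go and the Falls Efficacy Scale under safety, and both are measured at 6 months. That widens the measurement, but D.9 plans no analysis of either.

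Finally, a GROUP2 comparison of its own PABC and control periods is tempting. Equal weekly recording is documented only for falls, and period effects are not controlled, so leaving out a within-person comparison of all adverse events is defensible.

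**Conclusion.** The point holds as a gap in planned estimation. The randomised Months 1-3 comparison is sound, but because it is the only safety analysis in D.9, 48 of 96 planned PABC person-months contribute to no planned event-rate estimate. Using them would raise the number of PABC-exposed participants from 16 to 32 and roughly halve the zero-event upper bound, from 17.1% to 8.9%. At an assumed 5% risk, the chance of seeing at least one case would rise from 56% to 81%.

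These figures assume groups of exactly 16, full delivery of PABC to both, and one common on-PABC risk across the two periods. With completers only, the bounds are 20.6% and 10.9%. The improvement is modest and cheap, and does not imply that H1.4 is wrong or that participants are unmonitored.

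**What to change.** Keep H1.4 as it is and add a descriptive analysis to D.9, for example:

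> AE, SAE and fall rates during the PABC period (GROUP1 Months 1-3, GROUP2 Months 4-6) will be estimated for all participants who start PABC. The proportion with at least one event will be given with an exact 95% CI, and events per participant with an interval that allows for repeat events within a person. All events and study-related events will be shown separately. These estimates will be reported beside the H1.4 comparison when the safety conclusion is stated.

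State in section A and D.9 which set of events H1.4 itself counts, since the two differ. If GROUP2's PABC and control periods are shown side by side, limit the display to falls and label it descriptive and open to period effects.

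The cost is one extra table from data already being collected. The limitation to state with it is that the pooled on-PABC rate has no concurrent control, so it describes frequency and does not attribute events to PABC.
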